CLINICAL TRIAL PROTOCOL

Therapeutic Effects of Constraint-Induced Movement Therapy on Young Children With Cerebral Palsy

NCT no.: NCT03858335

Protocol ID: 2015-06-100-008

Date of the document: September 29, 2019

Background

Cerebral palsy (CP) occurs when the immature brain develops non-progressive lesions due to multiple causative factors, resulting in impaired motor and postural function.¹ Unilateral CP, which accounts for nearly 30% of all cases,² is characterized by sensory and motor impairment on the unilateral side. Children with unilateral CP tend to only use the non-paretic side after discovering that it is more effective and efficient in performing tasks, even though impairment of the paretic hand is mild, which does not prevent them from performing daily tasks.³ This so-called “developmental disregard”⁴ can be reduced by constraint-induced movement therapy (CIMT). CIMT is a therapy that forces the use of the paretic upper limb by restraining the non-paretic limb. To demonstrate the effect of CIMT on developmental disregard, evaluating the amount of paretic arm use in real-life situation is important. For this reason, Pediatric Motor Activity Log (PMAL),⁵ a questionnaire-based test that assesses the real-world use of the paretic upper limb, has been frequently used in CIMT studies.⁵⁻⁷ However, PMAL is a parental-rating scale; thus, it may not be completely objective. In addition, several standardized assessments that evaluate the motor function of upper extremities are available, but those tools only focus on measuring a child’s capacity to use the paretic upper extremity. Actual use of the paretic upper limb in the real world differs from its motor capacity.⁸

Accelerometer is an objective instrument used to assess physical activity in structured and unstructured settings in the general pediatric population.⁹ This tool has become the preferred method for objectively examining real-world physical activity owing to its affordability and portability. Recent study has suggested that ActiGraph accelerometer is a valid and reliable tool for children with CP¹⁰ including toddlers.¹¹ Coker-Bolt et al. applied accelerometers to determine the effects of CIMT on paretic arm use in real-life situations, but 7/12 participants showed no increase in the amount of paretic arm use after CIMT.¹² A plausible explanation

for this unexpected result was the age of participants (mean: 4.9 years). An animal study confirmed that early CIMT during the corticospinal tract (CST) refinement period is effective for motor performance, and no longer effective once the CST refinement period has passed.¹³ Considering that the myelination of the CST is complete by 3 years of age in humans,¹⁴ application of CIMT in infants and toddlers is expected to yield different results.

Study Objective

The main purpose of this study is to determine whether modified CIMT (mCIMT) with continuous restraint is feasible for infants and toddlers with unilateral CP and is effective in enhancing the amount of paretic arm use in the real world. The study is based on the hypothesis that mCIMT would be feasible and facilitate better use of the paretic hand in the real world.

Methods

Participants

Informed consent forms were obtained from the children's parents or legal guardians before enrollment. From November 2015 to October 2018, we prospectively enrolled consecutive children with unilateral CP who were admitted to a tertiary hospital in Seoul, Republic of Korea. The inclusion criteria were (1) age 7 to 36 months and (2) diagnosed with unilateral CP due to central nervous system lesions. The exclusion criteria were (1) severe cognitive dysfunction that rendered them unable to perform simple tasks (e.g., reaching, grasping), (2) untreated seizures, (3) visual or auditory problems interfering with treatment, and (4) prior history of musculoskeletal disorders. We asked parents to report if their child presented any adverse events such as sleep disorder or skin rashes. This study excluded

participants whose potential risks exceeded the efficacy, and those with absence rates >20% (>3/15 sessions).

Study design

Thirty-two potential participants received a face-to-face screening assessment. A sample of 32 eligible participants were randomized into the mCIMT or control group by permuted block randomization with block length 4 (N=16 per group). The evaluations were performed on two occasions: at baseline and immediately after the intervention. Only children in the control group who participated in the accelerometer study (N=4) underwent an additional evaluation to determine whether changes in the values of accelerometers were due to mCIMT or whether they changed as they grew older. The measures were conducted by occupational and physical therapists with more than 10 years of experience who were blinded to the intervention.

Modified constraint-induced movement therapy (mCIMT)

Each child in the mCIMT group wore an individually tailored plastic forearm resting splint that is detachable on his or her non-paretic side for 3 weeks. The therapist removed the splint for 15 minutes before each mCIMT session to allow for active range of motion of the non-paretic upper limb and to assess non-paretic hand function by the grasping domains of PDMS-2. The participants could take off the splints during washes and while in sleep. In addition, parents were asked to take off the splints and report if adverse events such as increase of stress/crying, sleep disorders, or skin rashes occurred. A standardized pediatric CIMT protocol, which is a technique to shape motor behavior with repetitive and concentrated training of the paretic upper limb according to Taub's and Deluca's protocol,^{15,16} was applied by an occupational therapist. The 15 treatment sessions occurred over a 3-week

period (excluding weekends) in the mCIMT group, for 2 hours each (30-hour dosage in total). The control group received no mCIMT protocol except for children who wore accelerometers; they received mCIMT protocol post-test. All subjects who participated in this study retained the occupational or physical therapy they received.

Statistical analyses plan

Baseline characteristics between the mCIMT and control groups will be compared using independent t-test, chi-square test, and Fisher's exact test. Differences between groups in standardized assessments at post-treatment will be compared with analysis of covariance using pre-treatment measures as covariates to determine the effect of mCIMT treatment. In addition, pre- and post-treatment outcomes of standard assessments will be compared using paired t-test in each group, and Wilcoxon signed-rank test was performed to compare pre- and post-treatment accelerometer outcomes (VMA, %MVPA, UR) of the eight children. Effect sizes will be expressed as partial eta-squared, which was calculated and reported as recommended by Cohen.¹⁷ The ranges for effect sizes are small ($.01 < \eta^2 < .06$), moderate ($.06 < \eta^2 < .14$), and large ($\eta^2 > .14$). Data analyses will be conducted using IBM SPSS Statistics for Windows, version 21.0 (IBM Corp., Armonk, NY).

References

2. Johnson A. Prevalence and characteristics of children with cerebral palsy in Europe. *Dev Med Child Neurol* 2002;44:633–640

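### Feasibility is the first-named aim but has no planned analysis, and the absence rule removes poorly attending mCIMT children after randomisation

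*Combined protocol and SAP*

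**What the plan says.** All references are to the combined protocol and SAP.

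- **Study Objective.** The main purpose has two parts, feasibility and effectiveness, and feasibility comes first: "determine whether modified CIMT (mCIMT) with continuous restraint is feasible for infants and toddlers with unilateral CP". The hypothesis keeps that order: "mCIMT would be feasible and facilitate better use of the paretic hand in the real world".
- **Methods, Participants.** After the entry criteria and a request that parents report adverse events, the text says that the study excluded "participants whose potential risks exceeded the efficacy, and those with absence rates >20% (>3/15 sessions").
- **Study design.** Allocation was by "permuted block randomization with block length 4 (N=16 per group"), 32 children in all.
- **Modified constraint-induced movement therapy.** The mCIMT group had 15 sessions, "for 2 hours each (30-hour dosage in total"). For adverse events, "parents were asked to take off the splints and report if adverse events" occurred. Control children had no mCIMT, except that those who wore accelerometers (four, per Study design) received it after their post-test.
- **Statistical analyses plan.** The planned analyses are baseline comparisons, a between-group analysis ("Differences between groups in standardized assessments at post-treatment will be compared with analysis of covariance"), within-group paired t-tests, a Wilcoxon signed-rank test on accelerometer outcomes in eight children, and partial eta-squared. None concerns attendance, completion, splint wear, adverse events or exclusions.

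**The concern.** One of the two stated aims has no analysis attached to it. That alone might be put down to brevity. The difficulty is that the plan also contains a rule acting on the data most relevant to that aim. Attendance is the only delivery measure with a number in the document, and children who fall below that number are removed. The plan does not say that they will be counted or described anywhere.

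If feasibility is later judged from the children who remain, the conclusion rests on a group selected for having attended. A reader could not tell a therapy that nearly every family managed from one that several did not, because both would look the same among retained children.

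**Working it through.** **1. The plan's own figures.** 3/15 = 20.0% and 4/15 = 26.7%, so more than 3 of 15 is the same rule as more than 20%. 15 sessions × 2 h = 30 h, as stated. The document gives no sample-size calculation, expected dropout or feasibility target to reproduce.

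**2. When the absence rule acts, and on whom.** The 15 sessions belong to the mCIMT course, which follows randomisation, so a fourth absence cannot be known before then. Up to the post-test only the mCIMT arm has such sessions. The rule could reach the four accelerometer controls during their later mCIMT course, but only after the between-group comparison point.

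**3. Direct consequence.** A retained mCIMT child has missed at most 3 sessions, so has attended at least 15 − 3 = 12 (12/15 = 80%, or 12 × 2 = 24 h). The proportion of retained children attending at least 12 of 15 is 100% by definition, for any true attendance rate.

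**4. Size under assumed numbers of failures.** The documents give no count, so the number *x* of the 16 randomised mCIMT children who meet the criterion is an assumption. Exact (Clopper-Pearson) 95% limits are the 0.025 quantile of Beta(x, n − x + 1) and the 0.975 quantile of Beta(x + 1, n − x). When x = n the lower limit is 0.025^(1/n) and the upper limit is 1.

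| Success among 16 (assumed) | All randomised to mCIMT | Retained children only |
|---|---|---|
| 16 | 16/16 = 100% (79.4 to 100) | 16/16 = 100% (79.4 to 100) |
| 14 | 14/16 = 87.5% (61.7 to 98.4) | 14/14 = 100% (76.8 to 100) |
| 13 | 13/16 = 81% (54.4 to 96.0) | 13/13 = 100% (75.3 to 100) |
| 12 | 12/16 = 75.0% (47.6 to 92.7) | 12/12 = 100% (73.5 to 100) |
| 10 | 10/16 = 62.5% (35.4 to 84.8) | 10/10 = 100% (69.2 to 100) |

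The first row shows no bias: if nobody was excluded, the two columns agree.

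**5. How likely it is that the rule removes someone.** If each child independently fails with probability *f*, the chance of at least one failure in 16 is 1 − (1 − f)^16.
- f = 10%: 1 − 0.9^16 = 81.5%
- f = 20%: 1 − 0.8^16 = 97.2%, with 16 × 0.2 = 3.2 failures expected

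**6. From session absence to exclusion.** Assume a per-session absence probability *p* and independent absences within a child. A child is then excluded with probability P(X ≥ 4), where X ~ Binomial(15, p).

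| p (assumed) | P(excluded) | Expected of 16 | Mean attendance, retained | True attendance |
|---|---|---|---|---|
| 5% | 0.5% | 0.1 | 95.1% | 95% |
| 10% | 5.6% | 0.9 | 91.1% | 90% |
| 15% | 17.7% | 2.8 | 88.2% | 85% |
| 20% | 35.2% | 5.6 | 86.2% | 80% |

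Independence is a simplification, since absences in young children may well cluster. The table shows that the effect runs from negligible to substantial over this range.

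**The case against.** The strongest reply is that the plan defines no feasibility percentage, so it cannot be said to bias one. A reader might infer that the plan would always show 100% feasibility, or that feasibility can only be confirmed. The documents do not support that. They do not say that feasibility will be calculated in retained children, or that exclusions will go unreported. Adverse events among retained children could still count against feasibility. The 100% result is exact only for attendance at the 12-of-15 level among retained children.

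A reader might also infer that every excluded child is one in whom mCIMT failed, and that every exclusion followed randomisation. Neither is established. No reasons for absence are given, and families miss sessions for causes other than intolerance. Such absence is still non-delivery, which a feasibility assessment should count, but it is not treatment failure. The clause on potential risks exceeding efficacy has no stated timing or decision-maker. It follows the entry criteria, and face-to-face screening is described, so it may be a screening judgement. It also follows the sentence on adverse events, so an on-treatment reading is possible too.

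Two further points stand. No excluded child is reported, so the actual effect may be nil. And a success criterion written now is late: enrolment ran to October 2018, treatment lasts three weeks, and the document is dated 29 September 2019. Attendance may already be known.

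The core remains. A main aim has no analysis, and a stated rule, followed exactly, sets aside the attendance failures that bear on it.

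**Conclusion.** The point holds in a limited form. Feasibility leads both the purpose and the hypothesis, nothing in the Statistical analyses plan addresses it, and the absence rule removes poorly attending mCIMT children after randomisation. Any attendance summary restricted to retained children is uninformative at the 12-of-15 level.

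The size of the bias is unknown and may be zero. The contrast of 13/13 (75% to 100%) with 13/16 (54% to 96%) depends on an assumed 3 exclusions and on 16 being the number randomised to mCIMT, as Study design states. Even perfect attendance, 16/16, leaves a lower limit of 79%, so an unqualified feasibility claim would outrun the data in any case.

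This should be corrected before a feasibility conclusion is reported. It does not prevent the efficacy analysis from going ahead, although the effect of the same exclusions on that comparison deserves its own consideration.

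**What to change.** Add a short feasibility paragraph to the Statistical analyses plan:

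- **Denominator:** all 16 children randomised to mCIMT. Children who meet the absence rule, or who were withdrawn after randomisation on risk grounds, stay in the feasibility assessment and count as not meeting the criterion.
- **Measure:** the proportion who missed no more than 3 of 15 sessions and were not withdrawn, with an exact 95% CI.
- **Exclusions:** every post-randomisation exclusion listed by arm and reason.
- **Descriptive reporting:** parent-reported adverse events and any reported splint removals.
- **Post-test mCIMT:** the four control children who received mCIMT after their post-test reported separately.
- **Stated limits:** the analysis was specified after enrolment ended. Attendance does not measure splint wear, and the plan describes no wear-time record, so this result alone does not show that continuous restraint is feasible. The conclusion should go no further than the interval allows.

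Applying the absence rule already requires attendance to be known, and parents were asked to report adverse events, so the main inputs should exist. How completely splint removals were recorded is not stated. No treatment, splint or withdrawal rule changes. The cost is one paragraph and one table, and a feasibility figure that may be less favourable.

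### Excluding children for missed sessions can affect only the mCIMT arm before the post-test, and no analysis set says whether they stay in the ANCOVA

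*Combined protocol and SAP*

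**What the plan says.** Methods, Participants lists four exclusion criteria that can be judged at entry. It then adds, separately, that the study excluded "participants whose potential risks exceeded the efficacy, and those with absence rates >20% (>3/15 sessions").

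Study design: "A sample of 32 eligible participants were randomized into the mCIMT or control group", 16 per group. On timing: "The evaluations were performed on two occasions: at baseline and immediately after the intervention".

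The mCIMT section places the 15 sessions over a 3-week "period (excluding weekends) in the mCIMT group, for 2 hours each (30-hour dosage in total"). Controls had no mCIMT, except the four who wore accelerometers, and "they received mCIMT protocol post-test". Both groups kept their usual therapy, for which no session count or attendance rule is given.

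Statistical analyses plan: "Differences between groups in standardized assessments at post-treatment will be compared with analysis of covariance using pre-treatment measures as covariates". It names no intention-to-treat, full or per-protocol set, and gives no handling for excluded children or missing post-tests.

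**The concern.** A rule based on attendance at treatment sessions can be applied only after randomisation and after treatment has begun. Here it can be met in one arm only. A control child who would have attended just as poorly has no sessions to miss and stays in.

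If the excluded children's post-tests are left out, the mCIMT group becomes the children who tolerated and kept up the programme, compared with all controls. Adjusting for the baseline score does not repair this when attendance is related to progress beyond what baseline predicts. If poor attenders would have done worse, the ANCOVA shows a benefit that mCIMT did not produce; if they would have done better, it understates the effect.

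The word for exclusion does not say whether the child leaves treatment, follow-up or analysis. Only the last, or a loss of follow-up that leaves no post-test, affects the comparison.

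**Working it through.** **Figures in the document.** 3/15 = 20%, so the percentage and the count agree. A retained child attended at least 15 − 3 = 12 sessions. 15 × 2 h = 30 h and 16 + 16 = 32 also agree. The plan gives no power calculation or significance level to reproduce.

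**Who can meet the rule before the between-group post-test.** mCIMT: up to 16 of 16. Control: 0 of 16, since the accelerometer controls' sessions come after that test.

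**Assumptions, none from the documents.** No true effect; 16 per arm; two-sided 5% test (2.5% in favour of mCIMT); higher score better; baseline-outcome correlation 0.7, so Y = 0.7X + 0.714e with 0.714 = √(1 − 0.49). The *k* lowest attenders leave the mCIMT arm only, and attendance correlates ρ with e.

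**Closed form.** Bias in outcome SD = ρ × 0.714 × *k* × m/(16 − *k*), where m is the mean depth below zero of the *k* lowest of 16 standard normals (1.766 for *k* = 1, 1.525 for *k* = 2).

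- *k* = 1: 0.3 × 0.714 × 1.766/15 = 0.025; with ρ = 0.5, 0.042.
- *k* = 2: 0.3 × 0.714 × 2 × 1.525/14 = 0.047; with ρ = 0.5, 0.078.

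**Simulation of the ANCOVA (40,000 runs per cell).**

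| Removed | ρ | Bias (SD) | Wrong claims for mCIMT |
|---|---|---|---|
| 1 | 0.3 | 0.025 | 3.1% |
| 1 | 0.5 | 0.043 | 3.9% |
| 2 | 0.3 | 0.044 | 3.7% |
| 2 | 0.5 | 0.077 | 4.6% |
| 2 | 0 | 0.00 | 2.5% |
| 2 | −0.5 | −0.08 | 1.3% |
| 4 | 0.3 | 0.088 | 4.9% |
| 4 | 0.5 | 0.144 | 7.5% |

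Repeat runs moved the biases by about 0.003 SD and the percentages by at most 0.4 points. With all 16 mCIMT children kept, bias is within 0.003 of zero.

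**Scale.** With 16 per arm the standard error is at least 0.714 × √(1/16 + 1/16) = 0.25 SD; estimating the covariate slope and losing a child or two brings it to about 0.26. The bias from one or two removals is therefore 0.025/0.26 to 0.078/0.26, or about 10% to 30% of one standard error.

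**How likely a removal is.** The documents give no absence rate. With independent absences at 5% or 10% per session, the chance that a child misses more than 3 of 15 is 0.0055 or 0.0556, and the chance of at least one such child among 16 is 1 − (1 − 0.0055)^16 = 8% or 1 − (1 − 0.0556)^16 = 60%. If absences cluster within child (assumed intraclass correlation 0.2), these become 68% and 93%. A range of 8% to 93% settles nothing; only the trial's own count can.

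**The case against.** The best defence is that the harm depends on two things the documents do not establish: that some child met the rule, and that exclusion meant leaving the analysis. The text reports 16 randomised per group and mentions no loss. These were children admitted to a hospital; if they were inpatients, frequent absence is less likely. Even with one or two removals the bias is well under one standard error. The 7.5% figure needs four of 16 removed at a correlation of 0.5, and at 10% absence the chance of four or more is 1% with independent absences (22% if clustered as above).

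Most of this stands, and it limits the size of the point. It does not remove it. The 16 per group is the number randomised, not the number analysed. The rule is stated and can affect one arm only, and nothing else in the plan says what happens to the child's data.

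Three stronger readings are tempting and not supported:

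- **That children were removed and the result favours mCIMT.** No removal is documented, and the direction depends on how attendance relates to outcome.
- **That the same objection reaches the accelerometer analysis of "Wilcoxon signed-rank test was performed to compare pre- and post-treatment accelerometer outcomes (VMA, %MVPA, UR) of the eight children", or the feasibility aim.** The accelerometer analysis is a pre-post test within children, not a randomised comparison, and the plan does not say whether eight is the count before or after exclusions. The plan defines no attendance measure of feasibility.
- **That the risk-benefit part of the exclusion sentence is also applied after randomisation.** Its timing and arm are not stated; it may be a screening judgement.

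**Conclusion.** The point holds in conditional form and should be fixed. The plan contains a post-randomisation exclusion that, before the between-group post-test, can apply only to the mCIMT arm, and no analysis set keeps those children in the ANCOVA. There is no bias if nobody was removed, if removed children were still tested and analysed, or if attendance is unrelated to outcome.

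Otherwise the likely size is modest, as tabulated for one or two removals, and grows with the number removed. Those sizes rest on the assumed correlations, the assumed 0.7 baseline-outcome correlation and a 5% two-sided test. Confidence is high that the rule is one-sided and the analysis set unnamed, and low on whether it changed anything in this trial.

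**What to change.** 1. State that the between-group ANCOVA includes every randomised child with a post-test, in the assigned group, whatever the attendance.
2. Keep the accelerometer controls' baseline and first post-test data in the control arm, whatever happens in their later mCIMT.
3. Make any set restricted to at least 12 of 15 sessions a secondary, per-protocol analysis.
4. Say whether exclusion means leaving treatment, follow-up or analysis.
5. Report removals by arm and reason.

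If removed children have no post-test, item 1 cannot bring them back. In that case add a sensitivity analysis: impute the missing values, shift them both up and down in steps, and report the shift at which the conclusion changes. For scale, shifting two children by one residual SD moves the estimate by about 0.714 × 2/16 = 0.089 outcome SD. Describe this as a sensitivity check, not a bound on the bias. Imputing from assigned arm and baseline alone adds nothing to the complete-case ANCOVA.

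The cost is a few sentences and a participant-flow count. The downside is a possibly diluted effect estimate, because children who received less of the programme stay in. Enrolment ended in October 2018 and the document is dated September 2019, so post-tests that were not done may be unrecoverable. No clinical decision about stopping treatment is affected.

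### Four accelerometer controls were re-evaluated to separate mCIMT from growth, but the plan has no between-group accelerometer analysis

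*Combined protocol and SAP*

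**What the plan says.** The Study Objective asks whether mCIMT is feasible and "effective in enhancing the amount of paretic arm use in the real world". The Background describes PMAL as a parent-rated measure of real-world use that may not be fully objective, and puts forward the accelerometer as the objective instrument.

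Under Study design, 32 children are randomized, 16 per group, with evaluations at baseline and after the intervention. "Only children in the control group who participated in the accelerometer study (N=4) underwent an additional evaluation", and its purpose is "to determine whether changes in the values of accelerometers were due to mCIMT or whether they changed as they grew older". The mCIMT section says that the control group had no mCIMT apart from the children with accelerometers: "they received mCIMT protocol post-test". It adds: "All subjects who participated in this study retained the occupational or physical therapy they received".

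The Statistical analyses plan has three outcome analyses:

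- Between groups: differences in "standardized assessments at post-treatment will be compared with analysis of covariance using pre-treatment measures as covariates to determine the effect of mCIMT treatment".
- Within each arm: "pre- and post-treatment outcomes of standard assessments will be compared using paired t-test in each group".
- Accelerometer: a Wilcoxon signed-rank test to "compare pre- and post-treatment accelerometer outcomes (VMA, %MVPA, UR) of the eight children".

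No section lists the assessments, names a primary outcome, or states an alpha or a multiplicity rule.

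**The concern.** The design collects the information needed to tell a treatment effect from maturation on the accelerometer, and the analysis plan then does not use it. The section has no analysis of the additional evaluation, none of the controls' untreated interval, and no between-group accelerometer comparison. For the objective measure of its efficacy aim, the plan therefore yields no estimate of the mCIMT effect.

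The children are 7 to 36 months old, and all kept their existing therapy. Arm use could rise over the study period without any contribution from mCIMT; the protocol raises growth itself. A pre-post gain in the eight children is open to that explanation.

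The second issue is smaller. The ANCOVA is a suitable method and is the only analysis tied to the mCIMT effect. But it is applied to an unstated number of assessments with nothing to say which one decides the question.

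**Working it through.** The plan gives no alpha, power, target effect or sample-size calculation, so there is no figure of its own to reproduce.

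**1. What each accelerometer analysis estimates.** Let g be the average change from growth and retained therapy over an interval, and e the mCIMT effect. Take g as the same in both arms and, for simplicity, in both of the controls' intervals. The plan does not say which interval the pre and post values bracket for the four controls, so take both readings, with an inferred split of 4 mCIMT and 4 control children.

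- All eight measured across their own mCIMT: average change = g + e.
- Controls measured across the untreated interval: average change = [4(g + e) + 4g]/8 = g + e/2.
- Between groups, baseline to post-test: (g + e) − g = e.

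With e = 0, both pre-post versions still equal g. Only the between-group contrast removes it.

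**2. Could the signed-rank test serve as the growth check?**

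- In eight children its smallest two-sided p is 2/2^8 = 0.0078. It can be significant, but for change over time.
- In the four controls alone the smallest p is 2/2^4 = 0.125. It can never reach 5%, so a non-significant result there would not show that growth was absent.

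**3. What a between-group comparison of 4 against 4 would deliver.**

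- t-based 95% half-width, in SD of change: t(0.975, 6 df) × √(1/4 + 1/4) = 2.447 × 0.707 = 1.73.
- Exact rank-sum test: C(8,4) = 70 arrangements, so the smallest two-sided p is 2/70 = 0.029 per outcome.
- Exact shift interval from the smallest to the largest pairwise difference: coverage 1 − 2/70 = 97.1%.
- Chance of a false significant result in favour of mCIMT: 1/70 = 1.4% per outcome, whatever the common gain. For any of three independent outcomes: 1 − (69/70)^3 = 4.2%.
- Power of the exact test by simulation: 14% for a difference of 1 SD and 49% for 2 SD.

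**4. The ANCOVAs.** Assume a two-sided 5% test per assessment, so 2.5% in favour of mCIMT, and m independent assessments with no true effect. The chance of at least one false finding in favour is 1 − 0.975^m.

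| m | Independent | Correlation 0.5 (simulated) |
|---|---|---|
| 1 | 2.5% | – |
| 2 | 4.9% | 4.6% |
| 3 | 7.3% | 6.3% |
| 5 | 11.9% | 9.4% |

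**The case against.** The strongest reply is that PMAL measures real-world use, is common in CIMT research, and may be one of the assessments analysed by ANCOVA. If so, the efficacy aim does have a randomized comparison. This stands as far as it goes. A reader might infer that the aim has no between-group test at all, and the document does not establish that. It names PMAL only in the Background, so it does not establish the opposite either. What remains is that no objective measure of real-world use has a planned between-group comparison.

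Three other stronger readings also go too far.

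- A reader might infer that the signed-rank test mixes treated and untreated children. The wording fits equally well with all eight being compared across their own mCIMT. Growth stays confounded either way.
- A reader might infer that pre-post gains will be claimed as efficacy. The plan ties only the ANCOVA to the effect of treatment. Error rates for a pre-post claim would also need an assumed growth gain, and the document gives none.
- A reader might infer that any one significant assessment will carry the claim. The plan states no such rule; it simply states no rule.

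It can also be said that eight children are too few for a useful comparison, and that a formal multiplicity procedure is a lot to ask of a 32-child study with a feasibility aim. Both have force. The first is why an estimate is proposed and not a test. The second is why an exploratory label is enough.

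**Conclusion.** The main point holds. The protocol gives the four accelerometer controls an extra evaluation to distinguish mCIMT from growth, and the Statistical analyses plan contains no analysis that does so. The planned pre-post test cannot do it under either reading of the interval. This is a gap in the analysis plan more than in data collection.

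The gain from closing it is modest in precision: about 1.7 SD of change either side, if the split is 4 and 4. That split is inferred from the four controls and the total of eight. Randomization protects the comparison only if selection of the eight did not depend on arm or response, and the document does not say how they were chosen.

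The multiplicity point is secondary. Its size, 4.9% to 11.9% against 2.5%, rests on an assumed alpha, an assumed 2 to 5 assessments, and independence. The plural supports more than one assessment and nothing more exact.

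Timing limits the remedy. Enrolment ended in October 2018, the document is dated September 29, 2019, and the accelerometer test is described in the past tense. A reader might infer that the analysis was chosen after the results were seen. The tense does not show that, since the rest of the section is mostly in the future tense, but it does mean that the timing must be disclosed.

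**What to change.** - Add a between-group estimate, with interval, of accelerometer change from baseline to post-test for each of the three outcomes, using the controls' untreated interval. Present it as an estimate and not as a confirmatory test.
- Report the accelerometer signed-rank tests and the within-arm paired t-tests as descriptive, not as evidence of efficacy.
- State which interval the pre and post values cover for the four controls, when their additional evaluation took place, how the eight children were chosen and how they split by arm.
- List every assessment analysed by ANCOVA, including whether PMAL is one. If a primary was named before the data were seen, say so and test it at two-sided 5%, with the rest secondary. Otherwise label the ANCOVAs exploratory and give estimates with 95% confidence intervals.
- Date the change and disclose its timing relative to data access.

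No new data are needed, provided the four controls have accelerometer readings at both ends of the untreated interval, as the stated purpose implies. The exploratory label costs no power but gives up a confirmatory claim. Holm's procedure is optional and does cost power: for an effect of 0.8 baseline-adjusted SD with 16 per arm, power at its first step falls from 59% to 47%, 40% or 33% with 2, 3 or 5 assessments.
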